APPENDIX Q. PUBLICATION POLICY

All unpublished information given to the investigator by the sponsor shall not be published or disclosed to a third party without the prior written consent of the sponsor.

The results of this study may be published or presented at scientific meetings. If this is foreseen, the investigator agrees to submit all manuscripts or abstracts to the sponsor before submission. This allows the sponsor to protect proprietary information and to provide comments.

The sponsor will comply with the requirements for publication of study results: “Recommendations for the Conduct, Reporting, Editing, and Publication of Scholarly Work in Medical Journals” (www.ICMJE.org). Publication of the results will occur in a timely manner according to applicable regulations. In accordance with standard editorial and ethical practice, the sponsor will generally support publication of multicenter studies only in their entirety and not as individual investigational center data. In this case, a coordinating investigator will be designated by mutual agreement.

Authorship will be determined by mutual agreement and in line with International Committee of Medical Journal Editors authorship requirements:

- substantial contributions to the conception or design of the work; or the acquisition, analysis, or interpretation of data for the work
- drafting the work or revising it critically for important intellectual content
- final approval of the version to be published
- agreement to be accountable for all aspects of the work in ensuring that questions related to the accuracy or integrity of any part of the work are appropriately investigated and resolved

The publications committee established by the sponsor will oversee this process. Additional publications may follow. Policies regarding the publication of the study results are defined in the financial agreement.

No patent applications based on the results of the study may be made by the investigator nor may assistance be given to any third party to make such an application without the written authorization of the sponsor.

APPENDIX R. GUIDANCE ON SAFETY MONITORING

Guidance on Monitoring Patients with Elevated Liver Function Tests

Liver enzymes (ALT, AST, GGT, and ALP) as well as total, direct, and indirect bilirubin will be measured at each study visit.

In any case of elevated ALT or AST to a level exceeding $\geq 2 \times$ the ULN (including patients whose baseline ALT or AST levels are $\geq 2 \times$ and $\leq 3 \times$ the ULN, who may be enrolled in the study), a thorough medical history and physical examination with a focus on liver disease should be undertaken.¹ In addition, the patient should be instructed to refrain from alcoholic beverages.

In case of symptoms compatible with drug-induced liver injury during the study, patients will be instructed to return to the study center for an unscheduled visit or to go to the emergency room to measure liver enzymes as soon as possible. Solitary elevations of total, direct, or indirect bilirubin, not accompanied by elevations of ALT or AST should be managed according to the discretion of the treating physician.

Elevation of Either ALT or AST to $\geq 3 \times$ ULN

Confirmation is required prior to IMP discontinuation in cases of elevation of either ALT or AST $\geq 3 \times$ ULN. (Note: In cases of elevation of ALT or AST $\geq 8 \times$ the ULN, no confirmation is required prior to IMP discontinuation, but the assessments below should be performed.) The following procedures should be followed:

- The day in which the abnormal value is received from the laboratory will be considered as day 0.
- The investigator should repeat the test for confirmation purposes (this may be performed in a local laboratory along with complete blood cell [CBC] count and differential to assess for eosinophilia; in general, in case a blood sample is sent to a local laboratory, the following assessments [and reference ranges] are mandatory: ALT [serum glutamic pyruvic transaminase], AST [serum glutamic oxaloacetic transaminase], ALP, bilirubin [total, direct, and indirect], CBC [with differential for eosinophil count, separate tube], and INR [separate tube; not to be sent in a confirmatory test]). The investigator should also question the patient regarding symptoms.

The abnormality will be regarded as confirmed in each of the following scenarios:

- the baseline value was within the normal range and ALT or AST is still $\geq 3 \times$ the ULN

¹ Thorough medical history with a focus on liver disease: personal or family history of liver disease; personal history of a systemic disease with potential liver involvement; exposure to alcohol, medications (prescription or over-the-counter), herbal preparations, dietary supplements, recreational drugs, special diets, or environmental chemical agents; potential exposure to infectious agents (eg, travel to developing countries, history of potential exposure to blood or blood products, high-risk sexual relations); and any additional information deemed relevant by the investigator. Physical examination, including signs of chronic liver disease.

- the baseline value was above the ULN and ALT or AST is $\geq 2 \times$ the baseline value

Additional Tests/Evaluations:

Upon confirmation of the abnormality as noted above, the following additional evaluations should be performed and results should be recorded in the CRF:

- serology for hepatitis A (antibody and immunoglobulins M and G), B (core antibody total, core immunoglobulin M, and surface antigen), and C viruses (central laboratory)
- serology for autoimmune hepatitis: anti-nuclear antibodies (titer), anti-smooth muscle antibodies, and anti-liver kidney microsomal antibodies (central laboratory); further testing may be required in case of a positive result for hepatitis B or C
- ultrasound examination of the liver and biliary tract at the investigator's discretion
- other diagnostic tests/consultations as deemed necessary by the investigator (eg, serology for hepatitis E virus in case of travel to endemic geography)
- observation and follow-up (to be performed after the abnormality was confirmed as above)

ALT or AST $\geq 3 \times$ ($>3.5 \times$ the ULN if the Baseline Value is $>2.5 \times$ the ULN) but $<5 \times$ the ULN

In addition to the above procedures required for any elevation to levels $>3 \times$ the ULN:

- Alanine aminotransferase, AST, GGT, ALP, total bilirubin, direct bilirubin, indirect bilirubin, CBC and differential (to assess for eosinophilia), and INR should be monitored on days 5 (± 2 days), 8 (± 2 days), 14 (± 3 days), and 28 (± 3 days). On at least 1 of these days, the test should be performed centrally. (The INR should be sent to a local laboratory only.)
- In cases where a local laboratory is used, the results should be recorded in the CRF, accompanied by the reference range of the relevant measurements.
- Should the abnormality ($\geq 3 \times$ the ULN in case baseline was within the normal range or $\geq 2 \times$ the ULN in case the baseline value was above ULN but still $<5 \times$ the ULN) persist further, the patient will be followed according to the investigator's discretion, but a blood sample for ALT, AST, GGT, ALP, and total bilirubin, direct bilirubin, indirect bilirubin should be sent to the central laboratory at least once a month.

ALT or AST $\geq 5 \times$ but $<8 \times$ the ULN

In addition to the above procedures required for any elevation to levels $>3 \times$ the ULN:

- Alanine aminotransferase, AST, GGT, ALP, total bilirubin, direct bilirubin, indirect bilirubin, CBC and differential count (to assess for eosinophilia), and INR should be monitored twice a week.

- At least for every other measurement, the tests should be sent to the central laboratory. The rest of the tests may be sent to a local laboratory. The INR should always be sent to a local laboratory.

ALT or AST $\geq 8 \times$ the ULN

In addition to the above procedures required for any elevation to levels $>3 \times$ the ULN:

- The IMP should be discontinued immediately, and the early withdrawal visit should be performed.
- For follow-up guidance, please see below section “Follow-Up of Liver Enzymes After Stopping Rules Are Met.”

Stopping Rules

In the following circumstances, the IMP will be discontinued immediately:

- any increase in ALT or AST to $\geq 3 \times$ the ULN, combined with INR $>1.5 \times$ the ULN or total bilirubin $>2 \times$ the ULN
- any increase in ALT or AST to $\geq 3 \times$ the ULN, which is accompanied by symptoms clearly associated with impaired liver function (eg, vomiting, nausea, fever, rash, and eosinophilia) and not deemed related to other diseases (eg, vomiting or nausea triggered by cluster headache)
- any increase in ALT or AST to levels ≥ 5 but $<8 \times$ the ULN, which is persistent for ≥ 2 weeks of repeated measurements
- any increase in ALT or AST to levels $\geq 8 \times$ the ULN
- in any case where monitoring of liver enzymes cannot be performed according to the protocol guidance

Follow-Up of Liver Enzymes After Stopping Rules Are Met

- A patient who meets the above criteria for discontinuation of the IMP should be invited to the investigational site to return the IMP. Early withdrawal visit activities should be performed as soon as possible.
- Liver enzymes should be monitored until normalization or stabilization of the abnormality, according to the discretion of the investigator.
- In any case, following the early withdrawal visit, the minimal follow-up period will be 30 days and will include measurement of liver enzymes at least once weekly (may be performed in local laboratory, with at least 1 test being sent to the central laboratory).

Every effort should be made to complete the additional tests/evaluations, as described above.

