3.3. Stopping Rules for the Study

During the conduct of the study, serious adverse events will be reviewed (see Section 7.1.5) as they are reported from the investigational centers to identify safety concerns.

The study may be terminated by the sponsor for any reason at any time. For example, the sponsor should terminate the study in the event of:

- new toxicological or pharmacological findings or safety issues invalidating the earlier positive benefit-risk assessment
- development of the IMP being discontinued

A patient may discontinue participation in the study at any time for any reason (eg, lack of efficacy, consent withdrawn, or adverse event). The investigator and/or sponsor can withdraw a patient from the study at any time for any reason (eg, protocol deviation as defined in Appendix C, noncompliance, or adverse event). In addition, patients with positive eC-SSRS findings or abnormal hepatic laboratory values (eg, alanine aminotransferase [ALT], aspartate aminotransferase [AST], alkaline phosphatase [ALP], gamma-glutamyl transpeptidase [GGT], bilirubin [total, direct, or indirect], or international normalized ratio [INR]) may meet criteria for discontinuation from the IMP as summarized in Appendix R.

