7.1. Adverse Events

7.1.1. Definition of an Adverse Event

Any untoward medical occurrence in a patient or clinical investigation subject administered a pharmaceutical product and which does not necessarily have to have a causal relationship with this treatment.

An adverse event can, therefore, be any unfavorable and unintended physical sign, symptom, or laboratory parameter that develops or worsens in severity during the course of this study, or significant worsening of the disease under study, or of any concurrent disease, whether or not considered related to fremanezumab. A new condition or the worsening of a pre-existing condition will be considered an adverse event. Stable chronic conditions (such as arthritis) that are present before study entry and do not worsen during this study will not be considered adverse events.

Accordingly, an adverse event can include any of the following:

- intercurrent illnesses
- physical injuries
- events possibly related to concomitant medication
- significant worsening (change in nature, severity, or frequency) of the disease under study or other pre-existing conditions
- drug interactions
- events occurring during diagnostic procedures or during any washout phase of this study
- laboratory or diagnostic test abnormalities that result in the withdrawal of the patient from the study, are associated with clinical signs and symptoms or a serious adverse event, require medical treatment or further diagnostic work-up, or are considered by the investigator to be clinically significant.

Note: Abnormal laboratory or diagnostic test results at the screening visit that preclude a patient from entering the study or receiving study treatment are not considered adverse events.

- all events of possible drug-induced liver injury with hyperbilirubinemia (defined as AST or ALT ≥ 3 times the ULN, plus either total bilirubin ≥ 2 times the ULN or INR > 1.5) or Hy's Law events require immediate study treatment cessation and reporting

as a serious adverse event. Refer to [Appendix R](#) for guidance regarding monitoring patients with elevated liver function tests.

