7.4. Clinical Laboratory Tests

All clinical laboratory test results outside of the reference range will be judged by the investigator as belonging to one of the following categories:

- abnormal and not clinically significant
- abnormal and clinically significant

A laboratory test result that is judged by the investigator as clinically significant will be recorded on the source documentation and the CRF as an adverse event, and monitored as described in Section 7.1.2. An event may include a laboratory or diagnostic test abnormality (once confirmed by repeated testing) that results in the withdrawal of the patient from the study, the temporary or permanent withdrawal of IMP or medical treatment, or further diagnostic work-up. Note: abnormal laboratory or diagnostic test results at the screening visit that preclude a patient from entering the study or receiving IMP are not considered adverse events.

In addition, potentially clinically significant values will be predefined by the sponsor for selected laboratory parameters and will be detailed in the statistical analysis plan.

Clinical laboratory tests (serum chemistry, hematology, coagulation, and urinalysis) will be performed at the time points detailed in Table 2. Clinical laboratory tests will be performed using the central laboratory. However, in case of abnormal coagulation during screening (run-in period), a local retest can be authorized by the sponsor on a case-by-case basis. Specific laboratory tests to be performed are provided in Appendix T.

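### Protocol Section 7.1.1 and Appendix R state the same mandatory liver stop with different INR and bilirubin criteria

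*Protocol*

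**What the plan says.** Section 7.1.1 of the protocol defines possible drug-induced liver injury as AST or ALT of at least 3 times the ULN together with total bilirubin of at least 2 "times the ULN or INR > 1.5". It adds that such events and Hy's "Law events require immediate study treatment cessation and reporting" as a serious adverse event, and it refers to Appendix R for monitoring guidance.

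Appendix R has its own list of stopping rules, introduced by "In the following circumstances, the IMP will be discontinued immediately". The first entry is ALT or AST of at least 3 times the ULN "combined with INR $>1.5 \times$ the ULN or total bilirubin $>2 \times$ the ULN".

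Section 3.3 names INR among the abnormal hepatic values for which patients "may meet criteria for discontinuation from the IMP as summarized in Appendix R".

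On where INR is measured, Section 7.4 says "Clinical laboratory tests will be performed using the central laboratory". Appendix R follow-up is different: "The INR should be sent to a local laboratory only" for ALT or AST from 3 to below 5 times the ULN, and "The INR should always be sent to a local laboratory" for 5 to below 8 times the ULN.

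**The concern.** Both passages command an immediate stop for the same laboratory pattern, so they should describe the same patients. One states INR as a fixed number and the other as a multiple of a laboratory limit. If that limit is above 1.0, some patients meet a mandatory stop in Section 7.1.1 and not the matching entry in Appendix R. A site that follows the Section 3.3 pointer and consults Appendix R alone would not see the 7.1.1 trigger. The Appendix R cut-off can also vary with the local laboratory that measures INR in follow-up, while the 7.1.1 cut-off cannot.

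What is at stake is consistent application of a safety stop across about 120 planned centers. No efficacy estimate, sample size or error rate depends on it.

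**Working it through.** The plan gives no figure to reproduce here. The check compares the texts and adds one line of arithmetic.

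**Criteria side by side (all protocol)**

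| Place | ALT or AST | Bilirubin | INR | Consequence |
|---|---|---|---|---|
| 7.1.1 | ≥3×ULN | ≥2×ULN | >1.5 | immediate stop; serious-event report |
| Appendix R, stopping rules | ≥3×ULN | >2×ULN | >1.5×ULN | immediate stop |
| 7.1.5.1 (Hy's law) | >3×ULN | >2×ULN | none | serious-event report |
| 7.1.7 | ≥3×ULN | ≥2×ULN | >1.5 | special-interest report |

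In the first two rows, bilirubin and INR are alternatives, combined with the transaminase criterion. Hy's law in 7.1.5.1 also requires no cholestasis and no other explanation, and 7.1.1 attaches the stop to it. SAP 8.3 and SAP Table 3 also use INR >1.5. Among these passages only the Appendix R stopping rule scales INR by the ULN.

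**INR gap.** The Appendix R cut-off is 1.5 × ULN, and the gap from 7.1.1 is 1.5 × ULN − 1.5. The documents give no INR ULN, so the ULN is an assumption:

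- ULN 1.0: 1.5 × 1.0 = 1.50, gap 0.00
- ULN 1.1: 1.5 × 1.1 = 1.65, gap 0.15
- ULN 1.2: 1.5 × 1.2 = 1.80, gap 0.30
- ULN 1.3: 1.5 × 1.3 = 1.95, gap 0.45

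The criteria agree only at a ULN of 1.0. Above that, the patient in the gap has ALT or AST ≥3×ULN, an INR above 1.5 but not above 1.5×ULN, bilirubin not above 2×ULN, and meets no other Appendix R stopping rule (such as the symptom rule or the ≥8×ULN rule).

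**Bilirubin.** ≥2×ULN and >2×ULN differ only at exactly 2×ULN.

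**Confirmation step.** Appendix R asks for confirmation before discontinuation when ALT or AST is ≥3×ULN, states an exception only at ≥8×ULN, and leaves INR out of the confirmatory sample. Section 7.1.1 and the Appendix R stopping list both make the combined criterion immediate. No passage says whether confirmation comes first for the combined criterion.

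**Two lesser wording points**

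- *Visits.* Appendix R has liver tests at every study visit. Table 2 marks clinical laboratory tests at visits 1, 2, 3, 5, 6 and 8, which is 6 of 9, and Appendix B lists none at visits 4, 7 or 9. Appendix J agrees: 6 samples × 6.5 mL = 39 mL, where nine visits would need 9 × 6.5 = 58.5 mL. The SAP 8.5 summary visits also fit Table 2.
- *Baseline values.* Exclusion r bars confirmed ALT, AST or ALP above 1.5×ULN. Appendix R says that patients with baseline ALT or AST from 2 to 3×ULN can be enrolled.

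**The case against.** The strongest reply is that little follows in practice. Appendix R never tells a site to continue below its cut-off, so a site that reads both passages can obey both. Section 3.3 does not make Appendix R the only source of stopping criteria. A patient in the gap is still reportable as a serious event under 7.1.1, within 24 hours under 7.1.5.3.1, and as a special-interest event under 7.1.7 by the same route. Injections are given at the site about every 28 days, so an immediate stop means withholding the next one, and the report will usually come first. All of this stands, and it limits the consequence. It does not make the two criteria the same.

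The laboratory question is also partly answered. Appendix R makes reference ranges mandatory for local samples and has local results recorded in the CRF with their range, which points to the reporting laboratory's ULN. Scheduled tests are central, so variation between laboratories arises only in follow-up.

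A reader might infer three stronger points, and the documents do not support them:

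- *That the confirmation step contradicts the immediate stop.* The combined rule can be read as the more specific one and so as governing. This is an ambiguity, not a proven contradiction.
- *That Appendix R admits patients whom exclusion r bars.* Exclusion r concerns confirmed values, apparently at screening. SAP 4.2 takes other baseline values as the last before the first dose, which can be the visit 2 sample. Against that, eligibility is reviewed again at visit 2 and Appendix R does not define its term. The conflict is apparent, not established.
- *That liver monitoring is inadequate.* Table 2, Appendix B, Appendix J and SAP 8.5 agree on the schedule, and Appendix R adds testing for patients with elevations or symptoms. The finding is one sentence at odds with that schedule.

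**Conclusion.** The inconsistency is real and should be fixed. Two mandatory stops for the same pattern use different INR scales and different bilirubin signs. Under the assumed INR ULNs of 1.0 to 1.3, the INR gap runs from nil to 0.45. It rests wholly on a ULN that the documents do not state, and they give no incidence, so the number of patients affected cannot be estimated.

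It would go too far to say that liver events would be missed or that patients would have to stay on treatment: reporting applies either way and neither passage directs continuation. The confirmation question is an ambiguity, the visit wording a plain but minor conflict, and the baseline wording an apparent one. No view is taken on which criterion, sequence or schedule is right.

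**What to change.** Reconcile Section 7.1.1 with the Appendix R stopping rules so that there is one combined criterion, on one INR scale and with one bilirubin sign. Check it against the Hy's law definition in 7.1.5.1 and the special-interest list in 7.1.7. State whether the Appendix R confirmation step applies to it. If INR stays a multiple of the ULN anywhere, say explicitly whose ULN is meant.

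In the same change, reconcile the liver-test visits in Appendix R with Table 2, Appendix B and Appendix J. Reconcile its baseline transaminase statement with exclusion r, and say which value baseline refers to.

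The values, sequence and schedule are for the sponsor's medical team. The cost is clarification-letter or amendment wording. There is no statistical cost, and no analysis changes unless the reconciled criteria alter the special-interest definition repeated in SAP 8.3.

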APPENDIX S. CLINICAL CRITERIA FOR DIAGNOSING ANAPHYLAXIS

As detailed by [Sampson et al 2006](#), anaphylaxis is broadly defined as, “a serious allergic reaction that is rapid in onset and may cause death.” Diagnostic criteria defined by the National Institute of Allergy and Infectious Disease/Food Allergy and Anaphylaxis Network during the second symposium on the definition and management of anaphylaxis, modified from [Sampson et al 2006](#), are as follows:

Anaphylaxis is highly likely when any 1 of the following 3 criteria is fulfilled:

5. Acute onset of an illness (minutes to several hours) with involvement of the skin, mucosal tissue, or both (eg, generalized hives, pruritus or flushing, swollen lips-tongue-uvula) and at least 1 of the following:
 - a. respiratory compromise (eg, dyspnea, wheeze-bronchospasm, stridor, reduced peak expiratory flow [PEF], hypoxemia)
 - b. reduced blood pressure or associated symptoms of end-organ dysfunction (eg, hypotonia [collapse], syncope, incontinence)
6. Two or more of the following that occur rapidly after exposure to a *likely allergen for that patient* (minutes to several hours):
 - a. involvement of the skin-mucosal tissue (eg, generalized hives, itch-flush, swollen lips-tongue-uvula)
 - b. respiratory compromise (eg, dyspnea, wheeze-bronchospasm, stridor, reduced PEF, hypoxemia)
 - c. reduced blood pressure or associated symptoms (eg, hypotonia [collapse], syncope, incontinence)
 - d. persistent gastrointestinal symptoms (eg, crampy abdominal pain, vomiting)
7. Reduced blood pressure after exposure to a *known allergen for that patient* (minutes to several hours):
 - a. adults: systolic blood pressure of <90 mm Hg or >30% decrease from that person’s baseline

In the event of suspected anaphylaxis, vital signs, including oxygen saturation and respiration rate, will be measured. Other assessments will be performed at the discretion of the investigator. As a precaution, each investigational site should have a resuscitation cart nearby.

